### 5.5.2 Deaths

A detailed table will be created showing the number of subjects who experienced one SAE leading to Death, the corresponding percentage of subjects and the number of events grouped by SOC and PT.

All deaths will be listed in a summary table.

CONFIDENTIEL / Ne pas diffuser sans autorisation de DBV

CONFIDENTIAL / Do not distribute without DBV authorization

	Statistical Analysis Plan	
	EPITOPE (V712-304) – Statistical Analysis Plan	
	Référence du Document /Document Reference : CCI	Page : 54 / 74

CCI

### 5.5.3 Local Skin Tolerance

#### Subject assessment

The severity of local skin reactions will be assessed on a daily basis by the parents/guardians in diaries during the whole treatment duration for Part B subjects. The following data from the subject's diaries will be summarized for itching, redness, swelling and any local reaction (itching, redness or swelling) by treatment group on the SAF:

- Number and percentage of subjects by maximum severity of skin reactions reported during the assessment period (all subjects / subjects with at least one reaction (grade  $\geq 1$ )).
- Number and proportion of days with a reaction reported (grade  $\geq 1$ ) during the assessment period.
- Number and proportion of days with a reaction reported Grade 0 / Grade 1 / Grade 2 / Grade 3 during the assessment period.

The proportion of days with a reaction reported will be calculated as:

$$\left( \frac{\text{Number of days with a reaction reported}}{\text{Number of days with a patch applied}} \right)$$

The number of days with a reaction reported and number of days with patches applied will be calculated based on application dates.

The above defined proportions will be calculated overall (Day 1 to Day 180 or Day 365) and for the following periods of time:

- Month 1 (Day 1 to Day 30),
- Month 2 (Day 31 to Day 60),
- Month 3 (Day 61 to Day 90),
- Month 4 (Day 91 to Day 120),
- Month 5 (Day 121 to Day 150),
- Month 6 (Day 151 to Day 180),
- Month 7 (Day 181 to Day 210),
- Month 8 (Day 211 to Day 240),
- Month 9 (Day 241 to Day 270),
- Month 10 (Day 271 to Day 300),
- Month 11 (Day 301 to Day 330),
- Month 12 (Day 331 to Day 365)
- Above Month 12 (> Day 365)

All data will be presented in a listing for SAF.

CONFIDENTIEL / Ne pas diffuser sans autorisation de DBV

CONFIDENTIAL / Do not distribute without DBV authorization

	Statistical Analysis Plan	
	EPITOPE (V712-304) – Statistical Analysis Plan	
	Référence du Document /Document Reference : CCI	Page : 55 / 74

CCI

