Appearance of any vesicles (grade 4) or ulcerative skin lesions or any other significant skin lesion seen under the patch while the patch is still applied on the skin or upon removal of the patch which could potentially lead to skin barrier disruption at sites of Viaskin® patch applications will be cautiously managed and follow-up.

Children's parents or guardians will be instructed to take a photograph in case of appearance of any vesicles or ulcerative skin lesions. In these rare specific cases, subjects should transiently discontinue patch application and return to the site for evaluation and treatment of the wounded area, as well as for the next patch application and adequate evaluation and treatment of the wounded zone.

Upon re-application of the new patch, the subject should remain at the site for 1 hour before being discharged. The site must contact the subject's parents/guardians by phone the day after this visit to ensure that no additional local blisters or vesicles developed and to confirm that the treatment can continue normally. The zone with vesicles or severe lesions should not be used for patch application until it has completely healed.

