**Table 2: Grading of Local Skin Reactions by the Parents/Guardians**

Grade Local	Itching Local	Redness Local	Swelling
1 = Mild	Itching easily bearable, painless, occasional scratching localized under the Viaskin® patch areas.	Mild redness (pale pink) localized under the Viaskin® patch areas.	Swelling localized under the Viaskin® patch areas.
2 = Moderate	Itching with intermittent scratching, possibly up to 2 minutes each localized under the Viaskin® patch areas.	Redness more intense (brighter pink to red), and/or redness extending beyond the Viaskin® patch areas.	Swelling extending beyond the Viaskin® patch areas.
3 = Severe	Spreading intense itching resulting in continuous scratching unbearable, interfering with daily activities. Requiring treatment.	Very intense redness/rash and/or redness largely extending beyond the Viaskin® patch areas.	Large swelling area extending beyond the Viaskin® patch areas.

[figure not shown]
These three pre-specified symptoms at patch application sites (itching, redness, swelling) will be graded on a daily basis in the diaries, during the first 6 months for part A subjects, and during the whole treatment duration for part B subjects. Subjects' parents/guardians will also be instructed to record in the diaries any other AEs (including any local skin reactions other than the 3 pre-specified ones at any time of the study, and any pre-specified local skin reactions occurring after the initial 6 months of treatment for part A subjects), and any concomitant medication or treatment taken for any type of AEs.

The site medical staff will review the subject's diary at each subject visit.

- For part A subjects: the 3 pre-specified symptoms solicited during the first 6 months will not be reported by the Investigators in the AE pages of the e-CRF, except if these symptoms are part of another concomitant disease or if these symptoms are leading to the subject's study discontinuation or serious AEs. Any other local skin reactions or any other type of adverse events spontaneously reported in the diaries will be reported by the Investigators in the AE e-CRF form. After month 6, any AE, including the 3 above symptoms, other local skin reactions

or any other type of AE will be reported in the dedicated section of the diaries. These AEs will be reported by the Investigators in the e-CRF.

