#### 8.6.5 Subject Diaries

Subject diary data will be summarized where appropriate and listed.

The number of days of itching, redness and swelling of Grade 1, 2, or 3 will be summarized separately by treatment group and overall (during the first 6 months for part A, and during the whole treatment duration for part B).

The most severe grades of itching, redness and swelling, documented in the diary, will also be summarized. The maximum grade of local reactions reported (itching, redness or swelling) will also be tabulated.

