If a subject did not bring back unused patches, the amount of patches that have been applied cannot be accurately assessed. During the Data Review Meeting, before database lock, each subject having unreturned kit will be evaluated and a decision will be taken whether the subject compliance should be considered as missing.

The study medication must be applied on the skin for 24 hours every day ( $\pm 4$  hours), except during the initiation of treatment, where the duration of application of the study medication will be progressively increased as follows:

- During the first week (from Day 1 through Day 7), the patches will be applied for 2 hours ( $\pm 30$  minutes) every day;
- During the second week (from Day 8 through Day 14), the patches will be applied for 4 hours ( $\pm 30$  minutes) every day;
- During the third week (from Day 15 through Day 21), the patches will be applied for 8 hours ( $\pm 1$  hour) every day;
- During the fourth week (from Day 21 through Day 28), the patches will be applied for 12 hours ( $\pm 2$  hours) every day;

CONFIDENTIEL / Ne pas diffuser sans autorisation de DBV

CONFIDENTIAL / Do not distribute without DBV authorization

	Statistical Analysis Plan	
	EPITOPE (V712-304) – Statistical Analysis Plan	
	Référence du Document /Document Reference : CCI	Page : 34 / 74

CCI

- From the fifth week onwards (Day 29), the patches will be applied for the entire 24 hours ( $\pm 4$  hours) every day.

The time to first 24 hours ( $\pm 4$  hours) patch application will be summarized by means of descriptive statistics (n, mean, SD, median, Q1, minimum, Q3, and maximum) and described using a Kaplan Meier curve.

The daily application duration (in hours) will be summarized descriptively using the subject e-diary data for the following periods:

- Overall,
- D1 to D7,
- D8 to D14,
- D15 to D21,
- D22 to D28,
- D29 to D90,
- D91 to D185,
- D186 to D275,
- D276 to D365,
- > D365,
- D29 to D365,
- > D29

If more than one patch is applied the same day, the daily duration considered is the cumulative application duration of these patches (if the end date/time of first patch is not documented, the application date/time of the next patch will be used for imputation).

The percentage of days with no patch application, per subject e-diary reported data, will also be tabulated, overall and for each of the above periods.

A patch will be considered as “applied” if the date and time of application is documented in the e-diary.

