## 7 MODIFICATION HISTORY

The modification history provides an overview of the status of the current document. It provides the cumulative accounting of changes including rationale and key details for major changes.

SAP Version	Date	Significant changes from the previous version	Author
1.0	02JUL2021	Creation	PPD
2.0	03SEP2021	Updates in: - Time-window at Month 12 - Confidence interval method changed for response rate difference in primary endpoint (Newcombe to Farrington-Manning)	PPD
3.0	10NOV2021	Updates in: - Lower bound of the 95% CI of the difference between the selected active treatment and placebo response rates changed from 15% to 10%	PPD

CONFIDENTIEL / Ne pas diffuser sans autorisation de DBV

CONFIDENTIAL / Do not distribute without DBV authorization

	Statistical Analysis Plan	
	EPITOPE (V712-304) – Statistical Analysis Plan	
	Référence du Document /Document Reference : CCI	Page : 66 / 74

[figure not shown]
CCI

		
 
- Clarification of intercurrent events handling and multiple imputation inferences for primary and secondary analyses
 
- The 2-sided 95% CIs of individual response rate corrected from Wald to Wilson.
 
- Details on imputation for incomplete date of birth added
 
- Safety overview table of TEAEs (analysis in subperiod of treatment post 4 years old added, overview repeated including APC)
 
- Anaphylactic reaction analyzed by LLT
 
- Modification in SAS® code lines for multiple imputation
 
- [REDACTED]
 
- Modification in peanut-specific IgE and IgG4 analyses
 
- Modification in local skin tolerance analyses (based on application dates)
 
- Specification of MedDRA version 20.1 used
 
	

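### SAP 5.5.3 dates diary reaction days by patch application, so reactions graded on patch-free days leave the day-based summaries, and SAP 5.11 does not list this change from the protocol

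*SAP*

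**What the plan says.** SAP 5.5.3 (Subject assessment) summarises parent-graded itching, redness and swelling over the whole Part B treatment. It gives the number and proportion of days with any reaction and the number and proportion at Grade 0, 1, 2 and 3. The proportions are repeated for each month. The denominator is "Number of days with a patch applied", and the dating rule for both counts is: "The number of days with a reaction reported and number of days with patches applied will be calculated based on application dates". SAP 5.3.8 treats a patch as applied "if the date and time of application is documented in the e-diary". The entry for version 3.0 in SAP Section 7 records the rule as "Modification in local skin tolerance analyses (based on application dates".

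Protocol 6.2.5 says, under Table 2, that the three symptoms "will be graded on a daily basis in the diaries", for the whole treatment duration in Part B. Protocol 8.6.5 then plans: "The number of days of itching, redness and swelling of Grade 1, 2, or 3 will be summarized separately". Neither is limited to days on which a patch was worn. SAP 5.11, which lists the differences from the protocol analyses, does not mention the application-date rule.

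**The concern.** The protocol foresees days without a patch, and some of them follow skin reactions. After vesicles, ulcerative lesions or similar lesions, Protocol 5.2.1 says "subjects should transiently discontinue patch application and return to the site for evaluation". Protocol 4.3.1 also foresees treatment interruptions for severe rash or dermatitis outside the patch area. A reaction can outlast the patch that caused it: Protocol 6.2.6 has investigators grade earlier application sites as well as the current one. If a parent grades a reaction during such a gap, the SAP rule gives that entry no date to attach to.

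Duration of local reactions as recorded in the diary is a stated safety criterion (SAP 3.3), and day counts are the only duration measure taken directly from the diary. A reader of those tables would take them to cover every graded day, as the protocol describes, when they cover patch days only.

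**Working it through.** **The rule applied to each kind of day**

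- Patch day, grade entered: in the numerator if Grade 1 or higher, and in the denominator. This is the intended use.
- No patch, grade entered: in neither count. Protocol 8.6.5 would count it if Grade 1 to 3.
- Patch day, no grade entered: in the denominator only, so in effect reaction-free. Grade 0 is a category of its own in SAP 5.5.3, so an empty entry is not the same as a recorded absence of reaction.

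**Notation.** Let a be the reaction days among P patch days, and b the reaction days among I patch-free days.

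- SAP count: a. Count over all diary days: a + b. Since b cannot be negative, the SAP count is never larger.
- SAP proportion: a/P. Proportion over all diary days: (a + b)/(P + I).
- All-days proportion minus SAP proportion = [I/(P + I)] × (b/I − a/P).

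The SAP proportion is therefore too low only when reactions are more frequent off patch than on patch. It is too high in the reverse case. The factor I/(P + I) makes the shift small over a year and larger in a month.

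For ungraded days, let U of the P patch days carry no grade. Then a/P = [a/(P − U)] × (P − U)/P. Relative to the proportion over graded patch days, this can only lower the figure or leave it unchanged. With U above zero, the four grade proportions no longer add to 100%.

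**Size.** The plan states no reaction rate, interruption length or expected proportion, so there is no figure to reproduce. The rows below are assumptions for one child in one window with 7 patch-free days.

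| Assumed case | a/P (SAP) | b/I | (a + b)/(P + I) | Shift, points |
|---|---|---|---|---|
| 30 days, 20% on, 100% off | 4.6/23 = 20.0% | 7/7 | 11.6/30 = 38.7% | +18.7 |
| 30 days, 50% on, 100% off | 11.5/23 = 50.0% | 7/7 | 18.5/30 = 61.7% | +11.7 |
| 30 days, 90% on, 50% off | 20.7/23 = 90.0% | 3.5/7 | 24.2/30 = 80.7% | −9.3 |
| 30 days, Grade 3 only | 1/23 = 4.3% | 5/7 | 6/30 = 20.0% | +15.7 |
| 365 days, 20% on, 100% off | 71.6/358 = 20.0% | 7/7 | 78.6/365 = 21.5% | +1.5 |
| 365 days, 90% on, 20% off | 322.2/358 = 90.0% | 1.4/7 | 323.6/365 = 88.7% | −1.3 |

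In the first row, 7 of 11.6 reaction days (60%) go uncounted. In an arm-level summary, children with no patch-free days contribute no shift, so the arm-level effect is smaller than these single-child figures.

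**The case against.** The strongest reply is that the rule may be only a dating convention. A 24-hour patch spans two calendar dates, and someone must decide which date its reaction belongs to. The e-diary specification is not in the documents, Protocol 6.2.5 speaks of reactions to the patch, and Table 2 describes most grades by reference to the patch area, so there may be no grades on patch-free days. This stands as uncertainty about how many entries are lost. It does not settle the matter: Protocol 6.2.5 and SAP 5.5.3 both describe daily grading over the whole treatment, and under the dating-convention reading an off-patch entry still has no application date. The plan should say what happens to it.

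A reader might go further and infer that the rule removes the worst reactions and so understates the difference between active and placebo. The documents do not support that.

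- For intense or severe local reactions without vesicles, Protocol 5.2.1 has the next patch applied the following day on the next zone, so those days remain patch days.
- Interruption for vesicles or ulcerative lesions is described there as rare. Protocol 5.2.2 also provides for interruptions for chicken pox, measles or active eczema on the back, which need not reflect patch reactions.
- Patch-free days leave both numerator and denominator, so the proportion has no fixed direction of error. An imbalance between arms in reaction-driven interruptions is plausible, but the documents give no figure for it.
- The reactions are captured elsewhere: diary maximum severity over the assessment period and the full diary listing (SAP 5.5.3); the three symptoms reported as adverse events at any severity (Protocol 6.2.5); TEAEs by maximum severity and duration and those leading to temporary discontinuation (SAP 5.5.1.3); local AESIs (SAP 5.5.1.1); and the investigator's worst grade (SAP 5.5.3).

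It can also be said that the protocol leaves detail to the SAP and that the version history records the rule openly. Both are true, but SAP 5.11 is where a reader looks for departures from the protocol. Finally, a per-patch-day rate is a legitimate tolerability measure, and a denominator of graded days may favour days on which parents wrote something. These are reasons to keep the present display and to report ungraded days, rather than to replace one denominator with another.

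**Conclusion.** The point holds within a narrow scope. As written, SAP 5.5.3 drops any reaction graded on a patch-free day from the number and proportion of reaction days, overall, by grade and by month, and keeps ungraded patch days in the denominator. The protocol's day count has no such restriction, and SAP 5.11 does not declare the change.

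Reaction-day counts can only be too low or unchanged; the proportion may be understated or overstated. The effect is small over 365 days when interruptions are short, and possibly material in monthly or high-grade rows. All sizes rest on assumed reaction rates and 7 patch-free days, and on the e-diary holding grades for patch-free days. This is a minor point about descriptive safety tables: no efficacy conclusion depends on it, and the other local-tolerance outputs stand.

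**What to change.** In SAP 5.5.3:

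- Keep the per-patch-day proportion as it is.
- Add the number and proportion of reaction days by grade and arm over all diary days with a grade recorded (Grade 0 to 3), from first patch to end of treatment.
- Show patch days and no-patch days separately in that display.
- Report the number of ungraded days by arm, and state how off-patch entries and ungraded days are treated in each display.

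Do not put all reaction days over patch days only. In the third row of the table that would give 24.2/23 = 1.05, a proportion above one.

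In SAP 5.11, list the application-date rule as a change from Protocol 8.6.5.

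The cost is a few sentences of SAP text and some programming on data already in the e-diary. The added figures may look slightly less favourable than the per-patch-day ones.

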### Investigator assessment

Examination of the skin at the site of patch application will be performed by the investigator at several visits:

- at Visit 4 the assessment will specifically be performed before patch application, at 30 minutes, 1 hour and 2 hours during patch application and 1 hour after patch removal.
- At each time point, the skin reaction will be graded by the Investigators on a scale of Grade 0 (negative) to Grade 4 (erythema, vesicles) and localization of the skin reaction (under the patch (A)/beyond the patch,(B)), see details in Table 7.

**Table 7 - Patch Application Site Skin Reaction Grading (Investigator)**

Skin Reaction	Grade if localized under the patch	Grade if extending beyond the patch	Grade regardless of localization
Negative	Grade 0	Grade 0	Grade 0
Only erythema, or erythema and infiltration	Grade 1A	Grade 1B	Grade 1
Erythema and few papules	Grade 2A	Grade 2B	Grade 2
Erythema and many or spreading papules	Grade 3A	Grade 3B	Grade 3
Erythema and vesicles	Grade 4A	Grade 4B	Grade 4

Grade 4B is considered as the most severe leading to 4B > 4A > 3B > 3A > 2B > 2A > 1B > 1A > 0.

The number and percentage of subjects with each grade will be presented by visit (and timepoint within visit for visit 4), both overall and by location of site reaction (under the patch / beyond the patch) by treatment group on the FAS.

Additionally, the worst grading overall (during the course of the trial) will be summarized as the number and percentage of subjects in each category on the Safety Set.

Patch site skin reaction data will also be listed on the Safety Set.

#### **5.5.4 Clinical Laboratory Evaluation**

Laboratory tests will be performed by a central laboratory. All laboratory data units will be converted to SI units if necessary.

The following laboratory parameters will be assessed at the analysis windows Baseline, Month 3, Month 6 and Month 12:

CONFIDENTIEL / Ne pas diffuser sans autorisation de DBV

CONFIDENTIAL / Do not distribute without DBV authorization

	Statistical Analysis Plan	
	EPITOPE (V712-304) – Statistical Analysis Plan	
	Référence du Document /Document Reference : CCI	Page : 56 / 74

CCI

- Hematology:
  - hemoglobin,
  - hematocrit,
  - platelets,
  - red blood cells,
  - white blood cells (with differential cell count (in %))
- Biochemistry:
  - alanine aminotransferase (ALT),
  - aspartate aminotransferase (AST),
  - total bilirubin,
  - total protein,
  - blood urea nitrogen,
  - creatinine

Clinically significant changes (abnormalities) in laboratory parameters, in the judgment of the Investigator, will be recorded as AEs and appropriate countermeasures taken.

In the event of unexplained abnormal laboratory test values of clinical significance, the tests should be repeated at a reasonable time point and followed up until they have returned to the normal range and/or an adequate explanation of the abnormality is found.

Those repeated assessments performed outside scheduled visits are taken into account for the analysis and should follow the rules described in section 5.2.7.

The following results will be tabulated for hematology and biochemistry tests on the safety set (in SI units):

- Descriptive statistics for each test result at each timepoint.
- Descriptive statistics for absolute changes from Baseline for each test result at time point.
- Common Toxicity Criteria for Adverse Events (CTCAE version 4.03) grade at each time point and shift from Baseline for each test result at each time point. CTCAE grades for hematology and biochemistry measures will be derived according to Appendix 8.3.
- Shift of test abnormalities (Low, Within normal range, High) between Baseline and each timepoint

All laboratory data will be listed. Values that are out of normal range will be flagged in the data listings.

Flags used are:

- Low (below normal ranges), based on the following original flags from the laboratory reports:
  - PL, L2 ("Panic Low")

CONFIDENTIEL / Ne pas diffuser sans autorisation de DBV

CONFIDENTIAL / Do not distribute without DBV authorization

	Statistical Analysis Plan	
	EPITOPE (V712-304) – Statistical Analysis Plan	
	Référence du Document /Document Reference : CCI	Page : 57 / 74

CCI

- TL, L1 ("Telephone Low")
- L ("Low")
- High (above normal ranges), based on the following original flags from the laboratory reports:
  - H ("High")
  - TH, H1 ("Telephone High")
  - PH, H2 ("Panic High")

When summarized in tables, all "High" flags will be merged together ("Panic High", "Telephone High", "High"); the same for the low flags as well.

In listings, "High" and "Low" flags will be reported.

Listings of all laboratory data will be provided by treatment group, and will include subject identifier, age, sex, weight and visit for the Safety set. Laboratory reference ranges will also be listed for the Safety set.

